An initial appointment will then be arranged with each consenting adult. They will complete standardised health, OSA risk and activity questionnaires and have anthropometric measurements taken. The subset with RHT who also score ≥ 9 on the Epworth Sleepiness Scale (ESS) will be identified as 'at risk for OSA' and, will have, 24h ambulatory blood pressure monitoring (24hABPM) to confirm TRHT. For the subset with TRHT on the second appointment cardiorespiratory fitness will be measured using a six minute walk test (6MWT), and an echocardiogram will be completed. Sleep and physical activity monitoring for seven (24h) days/nights will then be undertaken using a wrist monitor to confirm sleep fragmentation. The outcome will be correlated with the ESS score to determine those at high risk of OSA.

As investigators will adhere to the new (2017) guideline for hypertension and include only those participants with TRHT, this will create a new knowledge dimension. The association between high risk of OSA and TRHT will be a key outcome measure. The outcomes from the echocardiogram, anthropometrics, activity parameters, and quality of life questionnaires will describe the population. The findings have potential to change the direction of research in the area, including opening the topic of TRHT to more debate and supporting modified guidelines for physicians and physiotherapists in managing the subpopulation with OSA and TRHT.

2. Background

Hypertension (HT) is a worldwide problem which affects at least one third of the adult population, numbering billions of people in the world.⁽¹⁾ Key determinants of the increasing prevalence of HT are increase in life expectancy, counterbalanced by factors such as an increase in both physical inactivity and obesity.⁽²⁾ Cardiovascular disease is the greatest cause of morbidity and mortality in New Zealand and the prevalence of HT in the adult population is over 30%, with ethnic disparities.^(3, 4) The Maori population is at a higher risk for HT compared to the other populations in New Zealand and has a higher use of antihypertensive medication - over 15% more than the New Zealand Europeans.⁽⁴⁾

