The population will comprise adults with resistant hypertension (RHT), based in the Dunedin region, aged 60 years and younger, who have been diagnosed with high blood pressure and are on three or more pharmacological agents of different classes including a diuretic. The population has been drawn from the Ministry of Health Pharmaceutical Collection Warehouse, via the Best Practice Advocacy Centre (bpac),⁽²³⁾ New Zealand.

The total number of adults with hypertension and being pharmacologically managed with three or more antihypertensive medications (estimated RHT) in New Zealand is 100,340; Southern District Health Board, 8425; and in the Dunedin region, 3184. The number of adults 60 years age or below in the Dunedin region with RHT is 559.⁽²⁴⁾

9. Eligibility Criteria

Inclusion criteria

- Age: 18-60 years inclusive
- Gender: all
- Able to communicate/follow instructions in English
- Based in Dunedin region
- Diagnosed with hypertension
- Prescribed three or more antihypertensive medications including a diuretic (RHT definition⁽⁹⁾).

Exclusion criteria

- Diagnosed with hypertension prescribed two or less antihypertensive medications
- Adults above the age of 60 years
- Diagnosed/known renal disease
- Females who are pregnant

10. Study Outcomes

Primary Outcome

The prevalence of TRHT in a population with RHT and the association of TRHT with high risk of OSA.

Secondary Outcome(s)

The correlation between increased Epworth Sleepiness Scale score and sleep fragmentation in the subset with true resistant hypertension.

11. Study Procedures

a. Recruitment of participants

Adults (18-60y) in the Dunedin region, [anonymized] on three or more pharmacological agents of different classes, and the general practices [anonymized] they are enrolled at, have been identified from the Ministry of Health Pharmaceutical Collection Warehouse, via the Best Practice Advocacy Centre (bpac),⁽²³⁾ New Zealand. The number of adults on the list is 559⁽²⁴⁾, [the list of names will remain de-identified to the research team as letters will be forwarded by General Practitioners].

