Following a briefing by researchers about the study at a scheduled meeting of the local General Practitioners Association, researchers will gain agreement from General Practitioners to distribute a letter to their patients identified from PWC database. The letter of invitation to participate in the study will be co-signed by [name] and Associate [name]. Inclusion criteria will be adults 18-60 years, who meet the definition for RHT⁽⁹⁾, have no known renal disease and are able to communicate in English. Based on the population with RHT in Dunedin region a sample size n=83, with 95% confidence interval and 10% margin of error, is required. The recruitment target is n=100 with the dropout rate of up to 20%.

A list of individuals who consent to participate in the study will be created and each will be matched with a random serial number generated by the computer (using MS Excel). NIH number/name and contact details will be included on the database but remain deidentified other than to the research group. The random ID number will be used in the study.

The proposed recruitment period is August 2018 to April 2019; 9 months

Step 1

For individuals identified with RHT.

August 2018 - invitation to participate in the study;

August 2018 – March 2019: initial recruitment, initial measurements, 24hABPM

Step 2

For the sub group identified with TRHT and high ESS score.

September 2018 – April 2019: Echo cardiogram, cardiorespiratory fitness test (6MWT) and 24h day/night activity monitoring for one week

October 2019 September 2020 – write up and publication

11b. Randomisation

The study is a descriptive observational trial.

11c. Study procedure

Step I – Initial recruitment

Potential participants will be invited to contact [name] with enquiries and to indicate their interest in participating in the study. The Principal investigator (PI), the PhD candidate, will provide each participant with an appointment time for the initial assessment where written informed consent will be obtained first. The session will be at the School of Physiotherapy. A summary of the stages of the study is outlined in Figure 1.

Step II – Assessment and measurements

Appointment 1:

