The PI will obtain the participant's demographic data (age; gender; ethnicity); general health and habits, physical activity level (initial assessment form – Appendix 1), quality of life (SF-36: Appendix 2) and OSA risk (ESS: Appendix 3), using self-administered questionnaires. Participants will use a tablet computer to complete this section which will take approximately 20 minutes. Data will then be downloaded onto the study data base (MS Excel).

The PI will then take the participant's resting blood pressure (office blood pressure – (BP)), heart rate, and peripheral saturation using standardised, calibrated equipment (NT1A Pulse oximeter, New Tech, Hamburg, Germany and Omron automatic digital blood pressure monitor, HEM 7322, Netherlands) and in accordance with the

ACC/AHA 2017 guidelines.⁽⁶⁾ Next, the PI will take the anthropometric (body weight, height and circumferences of neck, waist, hip,) measurements of the participant using standard guidelines⁽²⁵⁾ and equipment; electronic weighing scale (kg) and stadiometer (cm), measuring tape (scale in cm); with two decimal point accuracy. The equipment will be calibrated as required. This section of the procedure will take about 15 minutes. The variables, body mass index (BMI) and waist to hip ratio will be calculated using simple formulas on MS Excel.

The subset with RHT who also score ≥ 9 on the Epworth Sleepiness Scale (ESS) will be identified as 'at risk for OSA', and will be fitted with 24h ambulatory blood pressure monitor on the non-dominant upper arm, at the Cardiology Research Laboratory, on 9th floor in Dunedin Hospital. The participant will be advised to undertake daily activities/sleep as usual over the next 24 hours.

Appointment 2:

On the following day the device will be removed at the same setting, the Cardiology Research Laboratory, and data downloaded to confirm TRHT or not. Where TRHT is confirmed the participant will have an echo cardiogram to confirm baseline left ventricular function (results to be interpreted by co-investigator cardiologist).

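### The ESS–sleep fragmentation correlation is defined for all TRHT, but both written routes to the actigraph first select on ESS, so the coefficient is attenuated against its stated target

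*Protocol*

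**What the plan says.** **Target of the correlation.** Objective 2 (Section 4) and the first secondary hypothesis (Section 5b) place it in the TRHT group and set no ESS limit. Section 10 gives the secondary outcome as "The correlation between increased Epworth Sleepiness Scale score and sleep fragmentation in the subset with true resistant hypertension".

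**Who gets ambulatory monitoring.** The protocol gives two answers.
- Section 11a, Step 1, headed "For individuals identified with RHT", lists "initial recruitment, initial measurements, 24hABPM" without an ESS condition.
- Section 11c, Appointment 1, sets one: "The subset with RHT who also score ≥ 9 on the Epworth Sleepiness Scale (ESS) will be identified as 'at risk for OSA", and it is this subset that "will be fitted with 24h ambulatory blood pressure monitor on the non-dominant upper arm". The Introduction has the same condition before "24h ambulatory blood pressure monitoring (24hABPM) to confirm TRHT".

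**Who gets the actigraph.**
- Section 11a, Step 2, which contains the week of activity monitoring, is "For the sub group identified with TRHT and high ESS score". It gives no cut-off for a high score; ≥ 9 appears only in the Introduction, Section 11c and Section 14.
- Section 11c, Appointment 2, conditions on TRHT alone: "Where TRHT is confirmed the participant will have an echo cardiogram to confirm baseline left ventricular function". The walk test and the wrist monitor follow.

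**The concern.** Sleep fragmentation is measured only by the wrist monitor. If that monitor reaches only participants with high ESS, the lower part of the ESS scale never enters the analysis, and the sample has been selected on one of the two variables being correlated. A correlation coefficient depends on the spread of both variables, so cutting the spread of one lowers it.

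The study could then report no correlation in TRHT when the lower ESS range was never observed. Section 11c goes on to use this correlation when identifying who is at high risk of OSA. Later analysis cannot repair the gap, because the missing actigraphy was never recorded. It is therefore a matter for the protocol and not a detail to leave to an analysis plan.

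**Working it through.** **1. The plan's own figure.** The only sample size is n = 83 (Sections 11a and 12a): 95% confidence, 10% margin, population 559. Taking p = 0.5, which the protocol does not state:
- n₀ = 1.96² × 0.25 / 0.10² = 96.04
- with finite population correction, 96.04 / (1 + 95.04/559) = 82.08, rounded up to 83.

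The figure reproduces. It is a precision calculation for a prevalence; no size is given for the correlation.

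**2. The routes, followed as written.**
- *Introduction and Section 11c:* ESS ≥ 9, then ambulatory monitoring, then TRHT confirmed, then actigraph. Everyone with confirmed TRHT already has ESS ≥ 9.
- *Section 11a:* ambulatory monitoring in RHT, then TRHT, then high ESS, then actigraph. Low scorers with TRHT are found but not given the actigraph.

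The selection falls at different points, but both routes end with TRHT and high ESS.

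**3. Effect on the coefficient.** The protocol gives no ESS distribution and no expected correlation, so both are assumed here: ESS roughly normal in TRHT, mean 6 to 10, SD 4 to 5. The cut ESS ≥ 9 is taken at 8.5 because scores are whole numbers.
- a = (8.5 − mean)/SD
- λ = φ(a)/(1 − Φ(a))
- u² = 1 + aλ − λ², where u is the ratio of the selected SD to the full SD
- r after selection = r·u / √(1 − r² + r²u²)

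Example, mean 6 and SD 4: a = 0.625; λ = 0.3282/0.2660 = 1.234; u² = 1 + 0.771 − 1.522 = 0.249; u = 0.50. For r = 0.40: 0.40 × 0.499 / √(0.84 + 0.16 × 0.249) = 0.1995/0.938 = 0.21.

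| ESS mean, SD | Share ≥ 9 | u | r 0.20 → | r 0.30 → | r 0.40 → | r 0.50 → |
|---|---|---|---|---|---|---|
| 6, 4 | 27% | 0.50 | 0.10 | 0.16 | 0.21 | 0.28 |
| 8, 5 | 46% | 0.58 | 0.12 | 0.18 | 0.25 | 0.32 |
| 10, 4 | 65% | 0.67 | 0.14 | 0.21 | 0.28 | 0.36 |

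The ratio of selected to full r runs from 0.101/0.20 = 0.50 to 0.362/0.50 = 0.72.

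**4. Check by simulation.** With whole-number ESS on 0–24 (mean, SD = 6, 4; 8, 5; 10, 5), r = 0.30 fell to 0.164, 0.189 and 0.204, and r = 0.50 fell to 0.294, 0.332 and 0.361. For r = 0.30, the slope of fragmentation on ESS was 0.080, 0.063 and 0.061 both before and after selection.

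**5. Number analysed.** Under the same assumptions 27–65% of the TRHT group would remain. The absolute number cannot be given: the protocol states no TRHT rate, and Section 12a calls the size of the cohort with TRHT and high OSA risk unknown.

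**The case against.** Several points on the other side have force.

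- **The Step 2 sentence is not the root cause.** A reader might infer that the bias comes from Step 2 naming TRHT plus high ESS while Appointment 2 names TRHT alone. The text does not support that. Under the Introduction and Section 11c, TRHT at Appointment 2 already means ESS ≥ 9, so the two descriptions cover in effect the same people. Rewording Step 2 alone would leave the selection in place. The conflict that matters is the ESS condition on ambulatory monitoring, set against the unconditional Step 1 and the all-TRHT objective.
- **The intended target may be the high-ESS group.** Section 10 speaks of an *increased* ESS score, which could be read as elevated ESS. If so, the coefficient in that group is not biased for its own target. But Objective 2 and hypothesis 5b have no such limit, so the protocol would still be inconsistent.
- **The slope is not attenuated.** This is correct, and Section 12b names regression, though for relationships with TRHT. Hypothesis 5b, Section 10 and Section 11c all speak of a correlation, which is the affected quantity.
- **A reading without truncation exists.** Taking Step 1 of Section 11a literally and then Appointment 2 of Section 11c literally would cover the full ESS range. No section describes that combination, and it ignores a condition stated in each.

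**Conclusion.** The point holds as an inconsistency with a statistical consequence. By either written route the plan computes a coefficient in TRHT with high ESS, while the objective and hypothesis ask about all TRHT. Relative to that target the coefficient falls to about 50–72% of its value (0.40 to about 0.21–0.28). This rests on a roughly linear relation with constant scatter, the assumed ESS means and SDs, and reading *high ESS* in Section 11a as ≥ 9. A non-linear relation could change the size.

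Two further inferences are not supported. A specific power for the correlation test would need a TRHT count that the protocol does not give. Nor can the attenuation safely be undone by a range-restriction correction based on the ESS spread of all enrolled participants: the correction needs the ESS spread of all TRHT, which is unobserved while the ESS condition on ambulatory monitoring stands. It would also answer a different question from an outcome restated for ESS ≥ 9.

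**What to change.** Reconcile the Introduction, Section 11a (Steps 1 and 2) and Section 11c so that they name one population for ambulatory monitoring and one for actigraphy. There are two consistent options.

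1. **Keep the all-TRHT target.** Perform ambulatory monitoring in all enrolled RHT participants, as Step 1 lists, and actigraphy in everyone with confirmed TRHT whatever the ESS score. Compute the correlation over the full ESS range. The cost is more ambulatory monitoring and actigraph sessions, within the 83–100 participants already planned. If all of Step 2 is widened, there are also more echocardiograms and six minute walk tests.
2. **Keep the ESS screen.** Restate Objective 2, hypothesis 5b and the secondary outcome as *in TRHT with ESS ≥ 9*, put that cut-off into Step 2, and draw no conclusion about all TRHT. This is a wording change and needs no extra data, but the question answered is narrower.

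Under either option, the Note in Section 11c, which refers to activity-monitor data from participants without TRHT, should be brought into line with whoever is to wear the monitor.

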Obstructive sleep apnoea (OSA) in adults has been correlated with the degree of blood pressure elevation above normal and thereby with the increasing risk of hypertension (HT).⁽¹³⁾ Thus, it is internationally accepted that OSA should be considered as a cause of both primary HT and secondary HT.^(1, 6, 7) The evidence has shown that OSA is linked with uncontrolled high blood pressure, more precisely, OSA has a close and strong relationship with RHT⁽¹⁾ and is cited as the most common secondary cause.⁽¹⁴⁾ Further, limited studies indicate, OSA has been associated with cardiac structure and function.⁽¹⁵⁾ However, relatively few studies have identified an association between OSA and TRHT.

It follows that since the severity of OSA is associated with major modifiable risk factors such as obesity and hyperaldosteronism in patients with RHT,⁽¹⁶⁾ reducing OSA through modifying the risk factor/s may be highly beneficial. Treatment for OSA is wide ranging and may include continuous positive airway pressure (CPAP).⁽¹⁷⁾ However, the goal of CPAP intervention is more to reduce symptoms rather than addressing the cause.⁽¹⁸⁾ Furthermore patient compliance is often low, due to the frustrations associated with the CPAP mask.⁽¹⁹⁾ Rather than just focusing on symptomatic management of OSA, it is suggested that new therapeutic strategies, that address OSA and HT simultaneously, may be more effective.⁽¹⁶⁾ In addition to CPAP management for OSA described above, increasing physical activity may be beneficial in treating both OSA⁽²⁰⁾ and BP⁽²¹⁾ as compliance with a prescribed physical activity programme can lead to a reduction in BP, and thereby, a reduction in the number of antihypertensive medications required by patients with HT.^(6, 7, 9, 22)

3. Aim of Study

To investigate the association between true resistant hypertension and high risk of obstructive sleep apnoea in a sub group of individuals diagnosed with resistant hypertension.

4. Objectives

To:

- determine the prevalence of true resistant hypertension (TRHT) measured by 24h ambulatory blood pressure monitoring in Dunedin based individuals with resistant hypertension (RHT);
- investigate the relationship between Epworth Sleepiness Scale scores and sleep fragmentation in the Dunedin based individuals identified with true resistant hypertension (TRHT);
- investigate the association between true resistant hypertension (TRHT) and high risk of obstructive sleep apnoea (OSA), in the Dunedin based individuals

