A statistician was consulted to confirm the calculation of the sample size based on the population with RHT in Dunedin region (559). Thus, the sample size is $n=83$, with 95% confidence level and 10% margin of error. The recruitment target is set at $n=100$ and with the dropout rate of up to 20%, the estimated sample size ($n=83$) is expected to be able to be fulfilled.

The cohort with true resistant hypertension and high risk of OSA is unknown for the Dunedin based population with RHT. An 18% response rate will be sufficient to achieve the target sample size ($n=100$) for the study.

12b. Statistical methods

Simple statistics (mean, standard deviation, range) will be used to describe the demographic data and the measurements (anthropometry /blood pressure/ /sleep/activity/cardiac parameters) of the population with RHT in Dunedin region and in the sub population with TRHT and high risk of OSA. The data for anthropometrics, blood pressure, activity and cardiac parameters will be compared with accepted international guidelines,⁽²⁵⁾ and questionnaires will be interpreted using standard descriptors.

The relationship between the anthropometry parameters, blood pressure, ESS score, cardiorespiratory fitness, and activity and sleep levels with TRHT will be determined using regression analysis.

The statistical package for social sciences (SPSS) version 25.0 or above for Windows (IBM SPSS version 25.0 or above), NY, USA⁽¹⁰⁾ will be used for the data analysis.

13. Ethical Considerations

The study to be conducted will conform fully with the principles of the “Declaration of Helsinki”, Good Clinical Practice (GCP) and within the laws and regulations of New Zealand. The study has been registered on the Australian New Zealand Clinical Trials Registry (ANZCTR). Ethical clearance will be obtained from the HDEC, New Zealand prior to commencing the study.

No identifiable information will be used in the study. For the identification of the cohort, the adults in the Dunedin region, who meet the criteria for RHT, on three or more pharmacological agents of different classes, including diuretic, have been identified (by bpac from the Ministry of Health Pharmaceutical Collection Warehouse and categorised to the various general practices. Letters supplied will be sent to those identified from their General Practitioner by linking names and addresses to national health numbers)

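### 24h ABPM is given only to participants with ESS ≥ 9, so the primary outcome, TRHT prevalence among all RHT adults, cannot be estimated as planned

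*Protocol*

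**What the plan says.** **What is to be estimated.** Section 10 gives the primary outcome as "The prevalence of TRHT in a population with RHT and the association of TRHT with high risk of OSA". The first objective in Section 4 is to "determine the prevalence of true resistant hypertension (TRHT) measured by 24h ambulatory blood pressure monitoring in Dunedin based individuals with resistant hypertension (RHT"). Hypothesis 5a concerns the same group. Section 12a describes a "calculation of the sample size based on the population with RHT in Dunedin region (559"), giving n=83 at 95% confidence with a 10% margin. Recruitment is set at 100, which it equates to an 18% response.

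**Who is monitored.** Two places spell this out, and both apply an ESS condition:

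- Introduction: the RHT participants who also score 9 or more on the ESS "will have, 24h ambulatory blood pressure monitoring (24hABPM) to confirm TRHT".
- Section 11c, Appointment 1: "The subset with RHT who also score ≥ 9 on the Epworth Sleepiness Scale (ESS) will be identified as" at risk of OSA, "and will be fitted with 24h ambulatory blood pressure monitor on the non-dominant upper arm".

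**A different account.** In Section 11a, Step 1 is headed as applying to individuals identified with RHT and reads "August 2018 – March 2019: initial recruitment, initial measurements, 24hABPM". It carries no ESS condition. High ESS first appears in Step 2, alongside TRHT, as a condition for the echocardiogram, walk test and activity monitoring.

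**The concern.** TRHT can be recognised in this study only through ABPM. If ABPM depends on ESS, outcome status is missing for everyone below the cut-off, and it is missing because of a variable the study itself treats as a marker of OSA risk. This is partial verification driven by the exposure of interest.

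Neither available denominator then answers the question. Dividing confirmed cases by all RHT participants treats every unmonitored person as not having TRHT. Dividing by those monitored gives the prevalence among sleepier RHT patients. That figure is too high for RHT as a whole if sleepiness goes with TRHT.

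The second half of the primary outcome suffers too. Everyone with known TRHT status would have ESS of 9 or more, so TRHT could not be compared across the ESS cut-off. The regression in Section 12b relating ESS to TRHT would run on a truncated ESS range.

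No analysis plan can repair this, because the missing measurements would never be taken.

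**Working it through.** **Inputs.** From the protocol: N = 559 (Sections 8 and 12a), 95% confidence, margin 0.10, n = 83, recruitment target 100. Assumed: p = 0.5 for the sample size, which the protocol does not state, and s, the share of RHT participants with ESS ≥ 9, which it does not give. I use s = 0.35 as the working value and 0.25–0.50 as the range, with 0.20 and 0.80 as extremes.

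**1. The plan's own figure.**

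n₀ = 1.96² × 0.25 / 0.10² = 96.04

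n = 96.04 / (1 + 95.04/559) = 82.08, rounded up to 83.

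The figure reproduces. The margin at 83 is 1.96 × √(0.25/83) × √((559 − 83)/558) = 0.099, or ±9.9 points. This requires an ABPM result for all 83, drawn from the whole RHT population.

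**2. The margin when only ESS ≥ 9 is monitored.** With m = 83s monitored from a stratum of N_s = 559s:

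margin = 1.96 × √(0.25/m) × √((N_s − m)/(N_s − 1))

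| s | monitored, of 83 | stratum size | margin | monitored, of 100 (no dropout) | margin |
|---|---|---|---|---|---|
| 0.20 | 17 | 112 | ±22.0 | 20 | ±19.9 |
| 0.25 | 21 | 140 | ±19.8 | 25 | ±17.8 |
| 0.35 | 29 | 196 | ±16.8 | 35 | ±15.0 |
| 0.50 | 42 | 280 | ±14.0 | 50 | ±12.6 |
| 0.80 | 66 | 447 | ±11.1 | 80 | ±9.9 |

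The stated ±10% is reached only if about 80% score 9 or more and nobody drops out. Even then it applies to the ESS ≥ 9 stratum, not to RHT.

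**3. Bias (illustration).** Let p₁ and p₀ be TRHT prevalence at ESS ≥ 9 and below 9. Then:

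- true prevalence = s·p₁ + (1 − s)·p₀
- all-RHT denominator gives s·p₁, so its bias is −(1 − s)·p₀
- monitored-only denominator gives p₁, so its bias is (1 − s)(p₁ − p₀)

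With s = 0.35, p₁ = 0.65 and p₀ = 0.50 (all assumed):

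- true = 0.2275 + 0.325 = 55.25%
- all-RHT denominator: 22.75%, bias −32.5 points
- monitored only: 65%, bias +9.75 points

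With s = 0.30, p₁ = 0.60 and p₀ = 0.40, the truth is 46% and the monitored-only figure is 60%, a bias of +14 points. If p₁ = p₀, the monitored-only bias is zero, but the data cannot show whether that is so.

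**4. What the data could say without assumptions.** The unmonitored share 1 − s could be anywhere from all negative to all positive. With 50% TRHT among those monitored, the bounds run from 0.5s to 0.5s + (1 − s). That is 15% to 85% at s = 0.30 and 25% to 75% at s = 0.50, before any sampling error.

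**The case against.** The strongest reply is that the protocol does not clearly intend the restriction. Step 1 in Section 11a, Objective 1 and hypothesis 5a all read as ABPM for everyone with RHT, and the flow diagram that might settle it is not available. On that view this is a contradiction in wording rather than a faulty design. It is right that the contradiction is part of the finding, and that the loss of estimability follows only if the ESS condition is applied. But the two places that describe the procedure both apply it, and staff at Appointment 1 would follow Section 11c.

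Other points are fair and limit how the numbers should be read:

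- The protocol does not say that unmonitored participants would be counted as negative. The −32.5 points shows what that denominator would do, not a stated plan.
- The ESS share and the two TRHT rates are assumptions, so the biases are illustrative.
- The protocol's association hypothesis has no direction. Upward bias is plausible from its background section, but it is not asserted there.
- Section 12a does not name the outcome that the ±10% refers to. Prevalence of TRHT is the natural reading.
- Prevalence within RHT with ESS ≥ 9 remains estimable. Prevalence in all RHT could be recovered only by assuming that TRHT is unrelated to ESS. That sits badly with a study designed to test whether TRHT is associated with OSA risk.

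None of this supplies ABPM results for participants below the cut-off.

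**Conclusion.** The plan is wrong as written. The Introduction and Section 11c restrict ABPM to ESS ≥ 9. The primary outcome, the first objective and the sample size all need it in RHT participants generally, and Section 11a lists it without the restriction. If the condition is applied, prevalence in RHT cannot be estimated without an untestable assumption, and TRHT cannot be compared across the ESS cut-off.

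The precision actually obtained from 83 participants would be about ±17 points at an assumed 35% with ESS ≥ 9, and between about ±20 and ±14 for 25–50%, for the subset only. The existence of the defect does not depend on these assumptions; only its size does. It needs correcting before enrolment, because ABPM not done at Appointment 1 cannot be recovered in the analysis.

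**What to change.** **Preferred.** Delete the ESS condition from the ABPM step in the Introduction and Section 11c, and fit the monitor to every enrolled RHT participant, as Section 11a Step 1 and the n=83 calculation already assume. Keep ESS as a recorded variable; Section 11a can still use high ESS to define Step 2. This gives ±9.9 points at n=83 and restores the range of ESS needed for the association. The cost is wording plus ABPM device-days for participants with ESS below 9, using a non-invasive device already in the study and within the number the sample size assumes. When Section 12a is edited, note that 100 recruits less 20% leaves 80, not 83, with a margin of ±10.2.

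**If the laboratory cannot monitor everyone.** Restate the primary outcome, Objective 1, hypothesis 5a and the title as TRHT prevalence among RHT adults with ESS ≥ 9. Withdraw any claim about RHT adults in general, and replace ±10% with the margin for the monitored subset. This costs wording only if that wider margin is accepted. To hold ±10% within the subset, recruitment would have to rise: n₀/(1 + (n₀ − 1)/(559s)), rounded up and divided by s, gives 58/0.25 = 232, 65/0.35 = 186 and 72/0.50 = 144 participants, against 100 planned. This option does not rescue the association between TRHT and ESS-based OSA risk, which would also have to be restated or dropped.
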